5.6. Other Exploratory Analyses

5.6.1. Risk Factor of Endoscopic Recurrence and Disease Recurrence

The analyses to identify risk factor of endoscopic recurrence and disease recurrence will be based on safety analysis set (based on actual intervention received).

All variables in interest will be included in univariate analysis. Univariate logistic regression model will be applied for endoscopic recurrence and univariate Cox proportional regression model will be applied for disease recurrence. The variables that are significantly (p value < 0.1) associated with each endpoint will be included in a full multivariable model for each endpoint. Stepwise selection, based on AIC, will be used to find the subset of variables to form a reduced multivariable model with only significant variable for each endpoint.

Variables in interest are listed as below:

- Second intra-abdominal operation for CD in the past 10 years
- Qualifying surgery was the patient's ≥ 3 intra-abdominal operation for CD
- Qualifying surgery was performed for a penetrating complication of CD
- Any history of perianal fistulizing CD provided that this has not been active in the 3 months before study start

- Cigarette smoker
- Kono-S anastomosis
- Mesenteric resection
- CD duration before first surgery (< 1 year, 1-10 yrs, > 10 years)
- Location of CD (Montreal L1 vs L2 vs L3 v L4)
- Crohn's phenotype: B3 (penetrating) vs other phenotypes

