9.4.4. Other/Exploratory Endpoints

The other/exploratory endpoints include but are not limited to the endpoints described in Section 3. A complete list of the other endpoints will be provided in the SAP. The testing of these endpoints will not be controlled for multiplicity and nominal p-values will be provided.

Other endpoints include:

- Change in PROMIS-Fatigue Short Form 7a score over 48 weeks
- Abdominal pain (AP score = 0) at each post baseline visit through Week 152
- Time to a flare of abdominal pain
- Clinical remission (CDAI <150) at each post baseline visit
- Change in PROMIS-Fatigue SF 7a at each post baseline visit through Week 152
- Change in PROMIS-29 score, both overall score and individual domain scores at each post baseline visit through Week 152
- Change from baseline in the WPAI at each post baseline visit through Week 152
- The number of participants not on corticosteroids and without disease recurrence at each post baseline visit through Week 152
- The number of participants not on corticosteroids and without endoscopic or disease recurrence at each post baseline visit through Week 152
- Endoscopic recurrence prior to or at Week 24
- Histologic score (as measured by Geboes scale/RHI/GHAS) at Week 48 ileocolonoscopy
- The number of participants with Geboes score over 3.1 at Week 48 ileocolonoscopy

- The number of participants with Geboes score of 2.0 or less at Week 48 ileocolonoscopy
- Clinical remission (CDAI <150) at Week 24 after initiation of guselkumab SC induction
- Clinical response (CDAI decrease of <100 points or CDAI <150) 24 weeks after initiation of guselkumab SC induction
- Disease recurrence (using definition described in Section 9.4.3) at Week 152
- Fecal calprotectin recurrence, defined by calprotectin of >200 μg/g with a 100 μg/g increase over baseline
- The change from baseline in fecal calprotectin concentration at all postbaseline visits through Week 152
- The change from baseline in CRP concentration at all postbaseline visits through Week 152

An additional exploratory analysis for risk factors of endoscopic and disease recurrence will be performed. A sensitivity analysis of the primary endpoint will be performed using a Rutgeerts score of > i3 as the definition for endoscopic recurrence.

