5.3.4. Subgroup Analyses

To evaluate the consistency of the primary analyses, subgroup analyses based on demographics (eg, age, sex, race, body weight, region), baseline characteristics (CD duration, involved gastrointestinal areas, number of CD related prior surgeries, CDAI score), baseline CD-related concomitant medication usage and biologic history (oral corticosteroids, oral 5-ASA compounds, immunomodulators(6-MP, AZA, or MTX), oral corticosteroids and immunomodulators, oral corticosteroids or immunomodulators prior biologic use), and potential risk factors for recurrence of active CD (number of risk factors for recurrence of active CD, the qualifying surgery was the patient's second intra-abdominal operation for CD in the past 10 years, the qualifying surgery was the patient's third (or more) intra-abdominal operation for CD, the qualifying surgery was performed for a penetrating complication of CD (ie, an intra-abdominal abscess, internal fistula, sinus tracts or intestinal perforation), the patient has any history of perianal fistulizing CD provided that this has not been active in the 3 months prior to study start, the patient is a cigarette smoker), the patient has Kono-S (antimesenteric functional end-to-end handsewn), the patient has mesenterectomy will be performed if sufficient data are available in the subgroup.

For subgroup analyses, the analysis sets are based on the **FAS**. Subgroup analyses will be performed when the number of participants in each subgroup permits. The following subgroup analyses will be performed:

- Statistical Analysis Plan CNTO1959CRD3007
- 1. The consistency of treatment effect for the primary endpoint will be evaluated for the subgroups defined in Section 5.8.5, using the **primary estimand**:

For each of the subgroups identified in Section 5.8.5, the rate (risk) difference of guselkumab vs placebo group and the associated p-values and 95% confidence intervals will be provided using forest plots. The difference in proportions, p-values and confidence intervals will be provided based on the same model specified in Section 5.3.3.1.

2. Using the primary estimand, an analysis of the primary endpoint will be performed for each region, country, and investigator site. This analysis will be descriptive and statistical testing will not be applied.

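### SAP 5.3.4 sets out to assess subgroup consistency without an interaction test, and SAP 5.6.1 selects risk factors by a p<0.1 screen that stepwise AIC does not tighten, with treatment arm left out

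*SAP*

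**What the plan says.** **Subgroups.** SAP 5.3.4 gives its purpose as evaluating whether the effect on the primary endpoint is consistent across the subgroups defined in SAP 5.8.5. The planned output is: "the rate (risk) difference of guselkumab vs placebo group and the associated p-values and 95% confidence intervals will be provided using forest plots". These come from the stratified Cochran-Mantel-Haenszel (CMH) analysis of SAP 5.3.3.1, repeated in each subgroup where numbers allow. SAP 5.8.5 lists 21 factors with 47 levels. Neither document plans a treatment-by-factor interaction test or gives a rule for calling the effect consistent.

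**Risk factors.** Protocol 9.4.4 says: "An additional exploratory analysis for risk factors of endoscopic and disease recurrence will be performed". SAP 5.6.1 supplies the method, using the safety analysis set by treatment received. "Univariate logistic regression model will be applied for endoscopic recurrence and univariate Cox proportional regression model will be applied for disease recurrence". Then: "The variables that are significantly (p value < 0.1) associated with each endpoint will be included in a full multivariable model for each endpoint". Then: "Stepwise selection, based on AIC, will be used to find the subset of variables to form a reduced multivariable model with only significant variable". It does not say what threshold counts as significant in the reduced model. Ten candidates are listed: eight binary, one with three levels and one with four. Treatment arm is not among them, nor are two of the stratification factors, baseline remission status and region.

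**The concern.** Whether an effect is consistent is a question about the difference between levels. A p-value inside one level tests whether the effect there is zero, and it depends heavily on how many participants that level holds. If the drug works equally well in everyone, the smaller levels will often miss significance, and a reader of the forest plot may take that for absence of effect.

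In the risk-factor analysis, the same data choose the variables and then supply their estimates and p-values, with no shrinkage, validation or allowance for selection. Factors retained by chance could be carried into a publication or a later trial's eligibility rules as if established. Leaving out the arm is a separate and smaller matter: the plan assumes it is a strong predictor, and the primary CMH test, the Cox models and the repeated-measures model elsewhere in the SAP all account for treatment and the stratification factors.

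**Working it through.** **Inputs.** 185 per arm, two-sided alpha 0.05, endoscopic recurrence 50% v 30%, disease recurrence 20% v 10% (protocol 9.2, SAP 3). Screen at p<0.1, ten candidates, two endpoints (SAP 5.6.1). 21 factors and 47 levels (counted from SAP 5.8.5: 5 demographic, 4 disease, 4 medication and 8 risk-factor items, with 12 + 11 + 8 + 16 levels).

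**1. Reproduce the plan's figure.** Power = Φ{[0.20 − 1.96·√(2·0.4·0.6/n)] / √[(0.5·0.5 + 0.3·0.7)/n]}. With n = 185 per arm: (0.20 − 1.96 × 0.05094)/0.04987 = 2.009, giving 97.8% against the stated 97.7%.

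**2. The same formula inside a subgroup, with the same true effect everywhere.**

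| Share of sample | n per arm | Power |
|---|---|---|
| 80% | 148 | 94.4% |
| 50% | 92.5 | 79.8% |
| 20% | 37 | 41.7% |

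- 50/50 factor, exactly one level significant: 2 × 0.798 × 0.202 = 32%.
- 80/20 factor: 0.944 × 0.583 + 0.417 × 0.056 = 57%.

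**3. All 21 factors.** Simulation: 1,500 trials of 370, assumed prevalences, independent factors.
- Uniform 50% v 30% effect: on average about 15 of 47 levels are non-significant, and about 11.5 of 21 factors are significant in some levels but not all. An interaction (heterogeneity) test at 0.05 flags about 1.2 of 21.
- At least one false flag among 21 unadjusted interaction tests: 1 − 0.95^21 = 66% under independence, 71% in the simulation, whose heterogeneity test is slightly liberal.
- No effect anywhere: about 2.3 of 47 levels are falsely significant (47 × 0.05 = 2.35).

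**4. The p<0.1 screen with every factor null and independent.** One endpoint: 1 − 0.9^10 = 65%, with 10 × 0.1 = 1.0 false pass expected. Both endpoints: 1 − 0.9^20 = 88%, with 2.0 expected.

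**5. Does AIC tighten it?** AIC keeps a term when its likelihood-ratio chi-square exceeds twice its degrees of freedom. That is p<0.157, 0.135 and 0.112 for 1, 2 and 3 df, all looser than 0.1. Simulation of the whole procedure (1,500 trials; a logistic model stands in for the Cox model):

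| Endpoint | Final model with ≥1 null variable, arm omitted | Same, arm forced in |
|---|---|---|
| Endoscopic recurrence | 66.8% | 66.2% |
| Disease recurrence | 69.6% | 67.5% |

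The standard error of each entry is about √(0.67 × 0.33/1500) = 1.2 points, so arm makes no detectable difference. If the undefined significance rule meant p<0.05 in the final model, 42-44% of final models (arm omitted) would still hold a null variable passing it.

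**6. What omitting arm costs.** For an assumed factor with 30% prevalence, a true conditional odds ratio of 2.0 becomes about 1.94 (endoscopic) or 1.97 (disease). In a separate 400-trial simulation with a true odds ratio of 2.2, power was 93.5% with arm and 91.0% without, each with a standard error of 1.2 to 1.4 points.

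**7. Information available.** The candidates use 8 + 2 + 3 = 13 df. Endoscopic events: 92.5 + 55.5 = 148, or 11.4 per parameter. Disease events: 37 + 18.5 = 55.5, or 4.3 per parameter.

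**The case against.** The strongest reply is that both analyses sit outside the error-controlled sequence. The risk-factor work is labelled exploratory in both documents, where a liberal screen is a defensible way to generate hypotheses. That stands, and it makes replacing stepwise selection outright debatable. It does not supply an interaction test where consistency is the stated question.

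Three stronger readings are tempting, and the documents do not support them:

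- **That the SAP judges consistency by within-level p-values.** It names no criterion and also plans risk differences and confidence intervals. The supportable statement is that no test of consistency is planned and the p-values invite misreading.
- **That leaving out arm produces chance risk factors.** Arm is randomised and so is independent of these pre-randomisation factors. Step 5 shows the false-retention rate is unchanged when it is added.
- **That chance findings will be reported.** SAP 1 says only four participants enrolled and the planned analyses no longer apply.

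Nor is treatment kept apart from every factor: the CMH test compares arms within the stratification factors, and the Cox models include treatment and those factors.

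The remedy also has limits. Unadjusted interaction tests would still flag at least one of 21 factors in about two-thirds of trials. The simulations assume independent factors and all-null candidates, whereas some listed variables overlap and SAP 5.3.4 regards several as potential risk factors. Correlation would lower the chance of at least one false retention; the expected number stays near one per endpoint.

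**Conclusion.** The point holds as a low-priority improvement to two exploratory analyses. The subgroup part is the firmer: the planned output does not test its stated question, and under a uniform 50% v 30% effect a 50/50 factor would look discordant about 32% of the time and an 80/20 factor about 57%. These figures use an unstratified two-proportion approximation; the totals across 21 factors also rest on assumed prevalences. The risk-factor part holds for selection: about 65-70% of final models per endpoint would contain at least one null variable if all candidates were null and independent, because AIC adds almost nothing after the screen. Omitting arm is a minor loss of precision with slight attenuation. No primary or hierarchical test is touched. With four participants enrolled, this bears only on the plan kept for reference and on any reuse of it.

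**What to change.** **SAP 5.3.4:** add one treatment-by-factor interaction p-value per factor, labelled exploratory and unadjusted for multiplicity. Keep the within-level risk differences and confidence intervals, and drop the within-level p-values.

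**SAP 5.6.1:** include arm and the three stratification factors in every model. First resolve two overlaps: the prior-surgery stratum with the two operation-count variables, and surgery for a penetrating complication with the B3 phenotype. Report estimates and confidence intervals for all listed factors, define significant, and show any stepwise-selected model only as exploratory.

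**Cost:** SAP wording and slightly more analysis work; no new data. Fewer factors will be nominally significant. Before overlaps are removed, arm (1 df), remission status (1), region (2) and prior surgeries (1) raise the model to 18 df, or 55.5/18 = 3.1 disease-recurrence events per parameter. Those estimates will be imprecise, and the report should say so.

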5.6.2. Cross over

The testing of these endpoints will not be controlled for multiplicity and nominal p-values will be provided.

5.6.2.1. Definition of Endpoints

- Clinical remission (CDAI < 150) at 24 weeks after initiation of guselkumab SC induction
- Clinical response (CDAI decrease of <100 points or CDAI <150) at 24 weeks after initiation of guselkumab SC induction
- Endoscopic remission (SES-CD of 3 or less) at 24 weeks after guselkumab SC induction
- Endoscopic remission (modified Rutgeerts score <i2a) at 24 weeks after guselkumab SC induction

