- b: If clinically appropriate and allowed by local regulations, the Week 156 visit can be done by telephone and no labs drawn.
- c: If a flare visit coincides with a scheduled visit, procedures for the scheduled visit should be performed, along with any additional procedures required by a flare visit. Flare visit blood tests are not required if performed within 2 weeks of the Flare visit.
- d: Early termination visits should ideally take place approximately 12 weeks after last study intervention administration, though if a patient intends to withdraw their consent sooner than this milestone the ET visit should be scheduled as needed to accommodate with the patient's intent.
- e: Blood collected from one venipuncture will be divided into multiple aliquots of serum for the measurement of guselkumab concentration, antibodies to guselkumab, and a back-up sample. Details will be provided in the Laboratory Manual.
- f: Ileocolonoscopy does not need to be repeated if an ileocolonoscopy for a flare visit occurred within 12 weeks of the visit date, unless patient and investigator wish to, for example due to subsequent change in clinical status.

Key: AE = adverse event; CD = Crohn's disease; CDAI = Clinical Disease Activity Index; CRP = C-reactive protein; CT = computed tomography; C-SSRS = Columbia Suicide Severity Rating Scale; eCRF = electronic case report form; ET = Early Termination; HBV = hepatitis B virus; HCV = hepatitis C virus; HIV = human immunodeficiency virus; IGRA = interferon gamma release assay; OTC = over the counter; PK = pharmacokinetics; PRO = patient-reported outcome; PROMIS = Patient-Reported Outcomes Measurement Information System; CCI ; TB = tuberculosis; WPAI = Work Productivity Impairment.

Cross Over (CO) Schedule of Activities (Follow if participant meets cross over criteria)

		`		•	Study Visits				
Study Procedure	COp	CO+8 wks	CO+16 wks ^c	Every 16 wks (up to Week 128)	Week 144 - Final Dosing Visit ^e	Week 152 - Final Efficacy Visit ^f	Week 156 -Final Safety Visit ^g	Early Terminati on Visit	Notes
Directed physical exam, with full physical exam where noted (F)	X	X	X	X	X	X(F)		X	Directed physical exam for abdominal mass and fistulas at all visits.
Urine pregnancy test	X	X	X	X	X	X			Must be performed at on-site visits prior to dispensing study intervention in participants of childbearing potential.

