CDAI assessment	X	X	X	Х	X	X		X	For calculation of CDAI. CDAI: The hematocrit value obtained during screening will be used to calculate CDAI at Week 0. For all other visits, the most recent hematocrit value obtained will be used to calculate the CDAI.
Weight (component of CDAI)	X	X	X	X	X	X		X	In kilograms (kg)
Fistula assessment	X	X	X	X	X	X		X	

					Study Visits	Week) ^a			
Study Procedure	COp	CO+8 wks	CO+16 wks ^c	Every 16 wks (up to Week 128)	Week 144 - Final Dosing Visit ^c	Week 152 - Final Efficacy Visit ^f	Week 156 -Final Safety Visit ^g	Early Terminati on Visit	Notes
Video ileocolonoscopy with biopsy and histology			X			X			XO+16 [OPTIONAL] May be performed between week 16 and 24. If performed on the day of the designated visit, the 7 days before the initiation of the colonoscopy preparation should be utilized to calculate CDAI scores for these visits. Final efficacy visit ileocolonoscopy does
									not need to be repeated if the XO+16 ileocolonoscopy occurred within 24 weeks of the visit date
Stool sample (fecal calprotectin)	X		X			X			
WPAI-CD	X		X			X		X	
PROMIS-29	X		X			X		X	
PROMIS Fatigue 7a	X		X			X		X	
Crohn's disease-related hospitalizations and surgeries	X	X	X	X	X	X	X	X	Items to be recorded are listed in the healthcare resource utilization worksheet.
Administer (or dispense) study intervention ⁱ	х	X	Х	X	X				All assessments described in this table are to be completed prior to study intervention administration, unless otherwise specified. PRO assessments should be completed first, and then any other clinical procedures, tests, or consultations. Cross over dosing: GUS 400 mg SC at CO, CO+4 (home dose), CO+8; and then CCI every 8 weeks (every other maintenance dose after the CO+16 visit will be home administration.
Record drug accountability	X	X	X	X	X			X	Participants will return study intervention packaging (cartons) when administered at home, for drug accountability, including any unadministered syringes.

CONFIDENTIAL – FOIA Exemptions Apply in U.S.

Footnotes:

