- a: Study visits should occur at the specified times post-cross over +/- 10 days. Note that while visits out of this window should be documented as a protocol deviation, performing them out of window is preferable to not performing them at all. If sufficient time has passed that it is now in-window for the next subsequent visit, it is advised to contact the medical monitor for assistance in how to best manage the situation. All assessments described in this table are to be completed prior to study intervention administration, unless otherwise specified. PRO assessments should be completed first, then C-SSRS and then any other clinical procedures, tests, or consultations.
- b: Laboratory assessments do not need to be performed if performed within 2 weeks prior to the CO visit
- c: Approximately 16-24 weeks after cross over, it will be determined, based on investigator's judgement, whether treatment with open-label SC guselkumab should be continued or not. It is recommended to include an ileocolonoscopy in this assessment. If a decision is undertaken to discontinue further study agent in the course of this assessment, an early termination visit should subsequently be performed.
- d: Additional follow up in cross over arm post Cross over Week 16 to occur every 16 weeks until the last dose of IP given.
- e: The final dose of IP should be given at the Final Dosing Visit, which will fall between Week 137 and Week 144 from the original randomization date. The final dose of IP should not be given past Week 144 from the original randomization date.
- f: The Final Efficacy Visit will occur 8 weeks after the Final Dosing Visit, between Week 145 and Week 152 from the original randomization date.
- g: The Final Safety Visit should occur 4 weeks after the Final Efficacy Visit, between Week 149 and Week 156 from the original randomization date. If allowed by local regulations and if clinically appropriate, the Final Safety Visit can be done by telephone and no safety laboratory blood samples drawn.
- h Blood collected from one venipuncture will be divided into multiple aliquots of serum for the measurement of guselkumab concentration, antibodies to guselkumab, and a back-up sample. Details will be provided in the Laboratory Manual.
- i Participants who discontinue study drug should have early termination visit as per protocol.

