cross over visit at a scheduled post-cross over visit. After the three dose induction doses, participants will receive open-label guselkumab dose will be given at a scheduled visit. Subsequent study visits will occur every 16 weeks during which the dose will be administered, with every other dose administered at home. The final dose will be given at the Final Dosing Visit, which will fall between Week 137 and Week 144 from the original randomization date. The Final Efficacy Visit will occur 8 weeks after the Final Dosing Visit, and will therefore fall between Weeks 145 and 152 from the original randomization date. The Final Safety Visit should occur 4 weeks after the Final Efficacy Visit (12 weeks after last dose of study agent), and will therefore fall between Weeks 149 and Weeks 156 from the original randomization date. If allowed by local regulation and if clinically appropriate, the Final Safety Visit can be done by telephone and no safety laboratory blood samples drawn. The study assessments for the Final Dosing Visit, Final Efficacy Visit, and Final Safety Visit will match the Week 144, Week 152 and Week 156 assessments in the original SoA, respectively.

Home Health Care and Telehealth Visits

Telehealth visits (conducted via phone or video conference) may be implemented by or with approval from the sponsor and per clinical judgement of the investigator for certain circumstances when warranted where feasible and permissible by local policy, regulations (as applicable) and for participants for whom there is no safety concern.

The nature of study procedures which may be performed with home health care and telehealth visits as circumstances necessitate will be defined by the Sponsor (see Section 10.8 for more details).

Sample Collection and Handling

The actual dates and times of sample collection must be recorded in the eCRF or laboratory requisition form. Refer to the SoA (Section 1.3) for the timing and frequency of all sample collections.

Instructions for the collection, handling, storage, and shipment of samples are found in the laboratory manual that will be provided. Collection, handling, storage, and shipment of samples must be under the specified, and where applicable, controlled temperature conditions as indicated in the laboratory manual.

Study-Specific Materials

The investigator will be provided with the following supplies:

- Investigator Site File (includes protocol and IB)
- Investigational Product Procedures Manual (IPPM)

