5.5.2. Analysis Methods

Unless otherwise specified, the exploratory endpoints listed and defined in Section 5.5.1 will be analyzed based on the FAS according to the randomized intervention group regardless of the intervention actually received.

All exploratory endpoints will be tested regardless of the significance of the primary and secondary endpoints; the testing of these endpoints will not be controlled for multiplicity. Nominal p-values will be presented.

Descriptive statistics (ie, N, mean, median, SD, IQ range, minimum, and maximum) will be used to summarize continuous variables. Frequency counts and percentages will be used to summarize categorical variables. Graphical data displays (eg, line plots) may also be used to summarize the data.

Binary Endpoints

The intercurrent events captured for binary endpoints specified in Section 5.3.2 will be applied to each of the above binary endpoints. Participants with ICEs in categories 1-4 will be considered to have unfavored outcome. For participants experiencing an ICE 5 and ICE 6, their observed values will be used, if available.

Participants with any missing data for an endpoint after accounting for the ICEs will be imputed as having unfavored outcome. Binary endpoints will be summarized with the number and frequency of participants who achieve the endpoint by treatment group. Treatment comparisons will be performed using CMH chi-square test stratified by clinical remission status at baseline (CDAI < 150, CDAI \ge 150), region (North America, Western Europe, rest of world) and number of prior surgeries (1 surgery versus > 1 surgery, with the qualifying surgery counting as 1 surgery). In case of rare events, the Fisher's exact test will be used for treatment comparisons.

Time-to-event Endpoints

The ICEs captured for time-to-event endpoints specified in Section 5.4.1 will be applied to each of the above time-to-event endpoints. Participants with ICEs in categories 1-3 will be considered to have unfavored outcome. For participants experiencing an ICE 4 and ICE 5, their observed values will be used, if available.

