6.12.2. CDAI Score Calculation Logic

• **Pre-Calculation Logic**

Step 1: Determine if a CDAI total score can be calculated.

Sufficient CDAI Daily Diary data/components AND CDAI Site Form completion for the current visit is required to calculate a total CDAI Score. CDAI score components are defined as:

- CDAI Daily Diary (participant diary) components:
 - 6. Number of liquid or soft stools each day for seven days
 - 7. Abdominal pain each day for seven days
 - 8. General well-being each day for seven days
 - 9. Fever (Yes/No)
 - 10. Anti-diarrhea medication (Yes/No)
- CDAI Site Form (site worksheet) components:
 - 1. Manifestations (arthritis/arthralgia, iritis/uveitis, erythema nodosum/pyoderma gangrenosum/aphthous stomatitis, anal fissure, fistula or abscess and other fistula)
 - 2. Abdominal mass evaluation
 - 3. Hematocrit
 - 4. Weight

For CDAI Daily Diary components, if there is not enough data in the previous 7 days (a minimum of 4 days of eligible diary data), then CDAI total score cannot be calculated. For CDAI Site Form components, if the CDAI Site Form has not been completed (and synced) on the tablet for the current visit, then CDAI score cannot be calculated.

Step 2: Determine if there is missing data for the CDAI Evening Diary components:

- For the current visit's CDAI Site Form, if the site user enters bowel preparation and video ileocolonoscopy dates (required if they answered, 'Yes' to "Has the participant had a video ileocolonoscopy since their last site visit?") (CDAI Site Form questions ebf0226f-b3a0-433a-82a7-aefd0e510c93_Question and 422e412e-1189-4b32-bcef-b7481d90dec9_Question), then any diary entries (if in the previous 7 days) between and including those 2 dates entered should be ineligible for the current calculation.
- A minimum of 4 days of diary data entry is required for components from the participant's CDAI Evening Diary in the 7 days prior to the current visit activation date.

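### The two crossover CDAI endpoints are set 24 weeks after open-label induction starts, when most crossover participants have no scheduled CDAI visit and would be scored as failures

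*SAP*

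**What the plan says.** **Endpoints.** SAP 5.6.2.1 lists four crossover efficacy endpoints, all at 24 weeks: two on CDAI (remission and response) and two endoscopic. The remission endpoint reads "Clinical remission (CDAI < 150) at 24 weeks after initiation of guselkumab SC induction". The CDAI pair also appears in SAP 1.1 and 5.5.1 and in Protocol 1.1, 3 and 9.4.4.

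**Visits.** The Cross Over Schedule of Activities in Protocol 1.3 has columns for CO, CO+8 and CO+16, followed by 16-weekly visits up to Week 128 and the final visits. Footnote d says: "Additional follow up in cross over arm post Cross over Week 16 to occur every 16 weeks until the last dose of IP given". Protocol 8 (Cross Over Visit) agrees: "Subsequent study visits will occur every 16 weeks during which the dose will be administered, with every other dose administered at home". CDAI is marked at each on-site visit through the Final Efficacy Visit and at Early Termination.

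**Endoscopy.** The ileocolonoscopy row notes: "XO+16 [OPTIONAL] May be performed between week 16 and 24". Protocol 6.5.1 says crossover participants should be reassessed by ileocolonoscopy about 16 to 24 weeks later.

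**CDAI derivation.** SAP 6.12.2 states that, besides enough diary data, "CDAI Site Form completion for the current visit is required to calculate a total CDAI Score".

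**Missing data.** SAP 5.6.2.2 has these endpoints analyzed in a similar way to 5.5.2 unless otherwise specified. For binary endpoints, 5.5.2 says: "Participants with any missing data for an endpoint after accounting for the ICEs will be imputed as having unfavored outcome". It also scores ICE categories 1–4 as unfavorable, and ICE 4 in SAP Table 7 is crossover to open-label guselkumab.

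**The concern.** The CDAI endpoints are fixed at a time when the schedule collects no total CDAI for most of the people they describe. If the missing-data rule is then applied, a participant who is in remission 24 weeks after crossover is counted as a failure because no visit took place. The remission and response rates would reflect the visit calendar more than the drug, and the objective of evaluating open-label induction and maintenance after recurrence could not be met on CDAI.

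**Working it through.** **1. The plan's own timing.** The Final Dosing Visit falls at Weeks 137–144 from randomization and the Final Efficacy Visit 8 weeks later: 137 + 8 = 145 and 144 + 8 = 152. This reproduces the stated Weeks 145–152.

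**2. Position of CO+24.** Maintenance doses are 8-weekly. CO+16 is on site and every other dose after it is at home, so CO+24 is a home dose and CO+32 is on site. With the ±10-day visit window of the crossover schedule (footnote a):

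| Time | Target day | Window |
|---|---|---|
| CO+16 | 16 × 7 = 112 | 102–122 |
| CO+24 | 24 × 7 = 168 | 158–178 |
| CO+32 | 32 × 7 = 224 | 214–234 |

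The gaps are 158 − 122 = 36 days and 214 − 178 = 36 days. By target day the neighboring visits are equally far away (168 − 112 = 56; 224 − 168 = 56), so there is no nearest visit to fall back on.

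**3. Who does have a visit at CO+24.** Let c be the crossover week. Crossover is possible after Week 8 and not after the Week 128 visit.
- Final Dosing Visit at CO+24: 137 ≤ c + 24 ≤ 144, so c = 113 to 120.
- Final Efficacy Visit at CO+24: 145 ≤ c + 24 ≤ 152, so c = 121 to 128.

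Listing every visit for each crossover week from 9 to 128 gives the same answer: Weeks 113–128 have one and Weeks 9–112 do not. Crossovers at Week 24 and Weeks 48–51 are in the second group. An Early Termination Visit also carries a CDAI, but it is for participants who stop and is not timed to CO+24.

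**4. Can the diary fill the gap?** Not for a total CDAI. The diary runs daily and the most recent hematocrit may be used, but the site form with the abdominal mass evaluation and weight is still needed. SAP 6.12.1 describes a partial CDAI, but the endpoints are defined on CDAI and no threshold is given for a partial score.

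**5. Is another visit mapped to 24 weeks?** No. The visit-window rule in SAP 5.1.1 counts from Week 0 and covers visits up to Week 56. It defines no crossover window.

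**6. Consequence.** No CDAI at CO+24, then 5.6.2.2 to 5.5.2, then unfavorable.

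**7. ICE 4.** Read literally, 5.5.2 scores the crossover itself as unfavorable. Table 7 covers events between baseline and Week 48, so a participant who crossed over before Week 48 would fail even with a CDAI in hand.

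**The case against.** Several counterarguments have force.

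- **The failure rule arrives by cross-reference.** SAP 5.6.2.2 does not state it, and its wording leaves room for a different reading. This stands as a limit on certainty. But 5.6.2.2 names no other rule for missing data, so a programmer following the text would reach 5.5.2.
- **The ±10 days is an operational window, not an analysis window.** True. An analyst could choose to map CO+16 or CO+32 to 24 weeks. The SAP does not authorize either, and the two are equally distant, so the choice would be made after the fact.
- **An assessment near 24 weeks is contemplated.** Footnote c of the crossover schedule and Protocol 6.5.1 place the continuation decision at about 16 to 24 weeks. That is right, but no CDAI is tied to it beyond the CO+16 visit.
- **The endoscopic endpoints are not in the same position.** A reader might infer that all four crossover endpoints fail in the same way. They do not: a permitted ileocolonoscopy reaches 24 weeks. Scoring participants without one as failures is a stated, conservative convention.
- **The stakes are small.** The endpoints are exploratory, without multiplicity control, and SAP 1 says the planned analyses no longer apply after four participants. This stands.

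**Conclusion.** The mismatch is real for the two CDAI endpoints. Anyone crossing over before about Week 113 has no scheduled CDAI at 24 weeks and, under the rule reached through SAP 5.5.2, counts as a failure whatever the response. This rests on the schedule as written, on 5.5.2 governing missing data, and on most crossovers occurring before Week 113. The last is likely, because confirmed endoscopic recurrence at Week 48 makes crossover mandatory.

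A reader might go further and infer a rate of zero among a known number, for example 185 × 0.50 + 185 × 0.30 = 148. The documents do not support that. The 148 is the planning number of endoscopic recurrences prior to or at Week 48, not a count of crossovers: crossover at Week 24 is discretionary, dropout is not deducted, and crossovers for disease recurrence continue to Week 128. Crossovers in Weeks 113–128 can also have a valid 24-week CDAI. The supportable statement is that most would be failures by default, without a figure.

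Primary and secondary endpoints, power and type I error are untouched.

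**What to change.** 1. Set the CDAI remission and response endpoints at the existing CO+16 visit, where CDAI is already scheduled, in Protocol 1.1, 3 and 9.4.4 and SAP 1.1, 5.5.1 and 5.6.2.1.
2. State in SAP 5.6.2.2 that ICE 4 does not apply to the crossover endpoints. Without this, participants who crossed over before Week 48 would still be scored as failures at CO+16.
3. For the two endoscopic endpoints, say that the ileocolonoscopy done 16 to 24 weeks after crossover is used, and report how many participants were not scoped. Keep the stated missing-data rule: restricting the denominator to those scoped would replace a conservative convention with a self-selected group.
4. Leave SAP 5.7.1 as it is. It counts study-agent administrations through 24 weeks after crossover, which needs dosing records and no CDAI.

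The cost is wording only, with no added visit or procedure. The price is a CDAI readout at 16 weeks, 8 weeks earlier than the stated objective. If 24 weeks matters, the alternative is an on-site CDAI assessment at CO+24, which adds a visit.
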